6.5 PHYSICAL EXAMINATION

Findings from the physical examinations will be summarized through 2 by 2 shift tables that, for each system or area examined, compare the normal/abnormal finding at screening to the normal/abnormal finding at the Final Visit. Table 6.5.1 gives the results of physical examination.

Listing 6.5.1 provides physical examination findings.

6.6 CONCOMITANT MEDICATIONS

A table (Table 6.6.1) summarizing frequencies of current use of concomitant medications will be presented for the safety population and its treatment group subsets.

Listing 6.6.1 provides the details of concomitant medications, and will summarize medications by WHO ATC and include information on dosage, route of administration, frequency, dates, and indication.

6.7 OTHER SAFETY ANALYSES FOR EXTRAPYRAMIDAL SYMPTOMS (EPS)

6.7.1 Simpson-Angus Scale (SAS)

Listing 6.7.1.1 provides subject-wise SAS scores for each visit. The occurrence of neurological side effects will be assessed by looking at the changes in scores from baseline to post-baseline visits.

For each item on the SAS scale, the number (and percentage) of subjects with a worse score at any post-baseline visit, compared to baseline, will be presented in Table 6.7.1.1.

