Subjects will return to the clinic on a weekly basis for a total of 8 to 11 visits following randomization (2 to 5 weeks of titration and 6 weeks of maintenance treatment). Safety,

*Safety Follow-up Phone Visit - 30 days post Final Study Visit

tolerability, and efficacy assessments will be performed at each visit. Blood and urine for clinical laboratory tests will be collected at Screening and at Weeks 2 and 6 of the Maintenance Period.

Blood will be drawn at trough for quantitative PK analysis at Weeks 2 and 3 of the Titration Period. At Week 2 of the Maintenance Period and the Final Visit, the subject's next maintenance dose of Study Medication (SM) will be administered in the clinic. The first PK draw will be a trough sample just prior to dosing. The dose will be administered, and a second draw will be performed between 1 and 3 hours post-dose.

Dose decreases will be permitted during the study for subjects randomized to Treatment 4 only, at the discretion of the Investigator in consultation with the Medical Monitor. Only 1 decrease to the next lowest dose (Treatment 3) will be permitted per subject. Benztropine will be permitted for the treatment of emerging extrapyramidal symptoms (EPS), at a starting dose of 0.5mg BID up to a range of 1 to 4mg/day.

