3.6.7 Other Special Tests for Extrapyramidal Symptoms (EPS)

Simpson-Angus Scale

The Simpson-Angus scale is a 10-item rating scale that is widely used for assessment of neuroleptic-induced Parkinsonism. It consists of 1 item measuring gait, 6 items measuring rigidity, and three items measuring glabella tap, tremor and salivation, respectively. This assessment will be administered at all post-screening study visits.

Barnes Akathisia Scale

The Barnes Akathisia scale is a rating scale for drug-induced akathisia and includes components for rating the observable, restless movements characteristic of akathisia, the awareness of restlessness, and any distress associated with the condition. This assessment will be administered at all post-screening study visits.

Abnormal Involuntary Movement Scale (AIMS)

The AIMS test is a rating scale used to measure tardive dyskinesia. There are 12 items that rate involuntary movements of various areas of the subject's body. This assessment will be administered at all post-screening study visits.

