6.7.2 Barnes Akathisia Scale (BAS)

Listing 6.7.2.1 provides subject-wise BAS scores for each visit. The occurrence of neurological side effects will be assessed by looking at the changes in scores from baseline to post-baseline visits.

For each item on the BAS scale, the number (and percentage) of subjects with a worse score at any post-baseline visit, compared to baseline, will be presented in Table 6.7.2.1.

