6.7.3 Abnormal Involuntary Movement Scale (AIMS)

Listing 6.7.3.1 provides subject-wise AIMS scores for each visit. The occurrence of neurological side effects will be assessed by looking at the changes in scores from baseline to post-baseline visits.

For each item on the AIMS scale, the number (and percentage) of subjects with a worse score at any post-baseline visit, compared to baseline, will be presented in Table 6.7.3.1.

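### The EPS scale tables take no account of benztropine use or unscheduled ratings, so they may understate EPS that was treated between visits

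*SAP*

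**What the plan says.** - **Treatment for EPS.** SAP Section 3.1: "Benztropine will be permitted for the treatment of emerging extrapyramidal symptoms (EPS), at a starting dose of 0.5mg BID". The sentence is not restricted to any treatment group.
- **How EPS is judged.** Sections 6.7.1 to 6.7.3 each state: "The occurrence of neurological side effects will be assessed by looking at the changes in scores from baseline to post-baseline visits". Table 6.7.1.1 then gives: "For each item on the SAS scale, the number (and percentage) of subjects with a worse score at any post-baseline visit, compared to baseline". Tables 6.7.2.1 (BAS) and 6.7.3.1 (AIMS) follow the same rule. None of the three subsections mentions benztropine.
- **When the scales are rated.** Section 3.6.7, for each scale: "This assessment will be administered at all post-screening study visits". Section 3.1 sets weekly visits, 8 to 11 of them after randomization.
- **Unscheduled visits.** Section 3.1.3 leaves the safety scales at such visits to the investigator's judgement, while adverse events are to be documented. Section 4 sends all unscheduled data to listings and keeps them out of the summaries.
- **Other displays.** Section 6.6 plans Table 6.6.1, "summarizing frequencies of current use of concomitant medications", by treatment group. Listing 6.6.1 carries dates and indication. Section 3.6.6 has the adverse event behind each medication recorded on the AE form, and Section 6.1.1 tabulates treatment-emergent events by treatment group.

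**The concern.** The primary objective (Section 2.1) is the safety and tolerability of four doses, and Section 6.7 is the only analysis devoted to EPS. A rating made while a child takes a drug for EPS is not the same evidence as a rating made without it, yet the tables treat the two alike. Starting benztropine for EPS is itself a sign that EPS occurred, and no EPS table uses it.

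The rule on unscheduled data widens the gap. If EPS appears between weekly visits, the worst score may be taken at the unscheduled visit where it is treated, or not taken at all. Either way it does not reach the table. Only the scheduled ratings do, and those after the event may be made on treatment. What is at stake is whether the scale tables give a fair count by dose.

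**Working it through.** The SAP gives no EPS rate, so there is no planned EPS figure to reproduce. Its one design figure, 60 completers from 72 at 17% dropout, checks (72 × 0.83 = 59.76) but has no bearing here. The check is a reading of the tabulation rule, followed by simple arithmetic.

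**1. When a child is counted.** A child counts as worse on an item if at least one summarized post-baseline rating exceeds baseline. Section 6.7 does not set aside the general rule in Section 4, so summarized means scheduled. A child with EPS is missed on an item only if all of these hold:
- the EPS began between scheduled visits;
- no scheduled rating on that item, before or after treatment, exceeded baseline;
- any worse rating was made at an unscheduled visit, or no scale was completed there.

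One worse scheduled rating, on or off benztropine, counts the child for good on that item.

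**2. Weight of one child.** With 72 randomized 1:1:1:1 within weight group (Sections 3.1 and 3.3), an arm has about 72/4 = 18 children. One masked child lowers an affected item's percentage by 1/18 = 5.6 points. If the denominator fell to the expected completers, 60/4 = 15, it would be 1/15 = 6.7 points.

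**3. Range of the effect.** For one item in one arm, let
- p = true share of children who worsen on the item;
- q = share of those whose EPS begins and is treated between scheduled visits;
- s = share of that subgroup whose scheduled ratings on the item never exceed baseline.

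Tabulated share = p(1 − q·s). Expected number missed = 18·p·q·s. All three inputs are assumptions; none is in the SAP.

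| p | q | s | Tabulated | Missed of 18 |
|---|---|---|---|---|
| 10% | 0.5 | 0.5 | 7.5% | 0.45 |
| 10% | 0.5 | 1 | 5% | 0.9 |
| 20% | any | 0 | 20% | 0 |
| 20% | 0.5 | 0.5 | 15% | 0.9 |
| 20% | 0.5 | 1 | 10% | 1.8 |
| 30% | 0.5 | 0.5 | 22.5% | 1.35 |
| 30% | 0.5 | 1 | 15% | 2.7 |

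Example: 0.20 × (1 − 0.5 × 1) = 0.10, and 18 × 0.20 × 0.5 × 1 = 1.8. The effect runs from nothing (s = 0) to complete masking (q = s = 1). Since q·s cannot be negative, this mechanism can only lower the count.

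**4. Do the other displays close the gap?** The adverse event tables are by MedDRA class and term, and Section 6.1 specifies no EPS grouping. Section 6.1.3 singles out deaths, serious events and events leading to discontinuation, dose reduction or interruption, but not EPS that needed treatment. Table 6.6.1 is not described as giving indication or timing; dates and indication are in the listing. No planned table shows, by arm, how many children were treated for EPS, or how many had either a worse score or such treatment.

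**The case against.** The strongest case for the plan has three parts, and much of it stands.

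*The any-visit rule is protective.* With weekly ratings, a single worse score counts the child. It is tempting to infer that every child treated before the next rating is tabulated as not worse. The rule does not produce that: it takes a clean scheduled record throughout.

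*The cases are not lost.* EPS that led to benztropine should appear in the adverse event tables by arm and, under Section 6.1.2, by weight group. Benztropine itself should appear in Table 6.6.1. A reader might infer that EPS is hidden from the trial's reporting. The documents do not support that; the gap is confined to the scale tables and to the missing link between displays.

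*Reporting scores as measured is legitimate.* Scales, events and medications may properly be shown separately, and this is neither an error nor a contradiction. A benztropine start also cannot be entered in an item-level table, because it identifies no worsened item.

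What remains is that the link must be assembled by hand from listings, and that unscheduled ratings are left out of the count to which they matter most.

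**Conclusion.** The point holds as a limited gap, worth closing because closing it is cheap. The scale tables can understate EPS by 5.6 percentage points of an arm per masked child on an affected item, taking 18 children per arm. The number of such children cannot be known from the SAP and may be nil.

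Two larger inferences go too far. One is that the dose gradient is flattened or that most cases in the highest-dose arms are hidden. That would require EPS to rise with dose and masking to be common; the SAP gives no figure for either, and it would affect the scale tables only. The other is an overall EPS rate per child that falls by so much. The planned tables are per item, so none of them prints such a rate.

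**What to change.** Keep Tables 6.7.1.1, 6.7.2.1 and 6.7.3.1 as item-level tables, with three changes to Section 6.7:

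1. State that unscheduled SAS, BAS and AIMS ratings enter the any-visit count, as an exception to the general rule in Section 4.
2. Add one table by treatment and weight group giving the number and percentage of children who (a) started benztropine for EPS, and (b) had either a worse score on at least one SAS, BAS or AIMS item or benztropine started for EPS. Identify (a) from the indication and dates planned for Listing 6.6.1 and the linked record on the AE form.
3. Flag in Listings 6.7.1.1, 6.7.2.1 and 6.7.3.1 every rating made while the child was on benztropine.

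The cost is some SAP wording, one more table and a listing flag, all from data already planned for collection. EPS percentages may come out slightly higher. No change to the permitted treatment is proposed.

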6.7.2 Barnes Akathisia Scale (BAS)

Listing 6.7.2.1 provides subject-wise BAS scores for each visit. The occurrence of neurological side effects will be assessed by looking at the changes in scores from baseline to post-baseline visits.

For each item on the BAS scale, the number (and percentage) of subjects with a worse score at any post-baseline visit, compared to baseline, will be presented in Table 6.7.2.1.

6.7.3 Abnormal Involuntary Movement Scale (AIMS)

Listing 6.7.3.1 provides subject-wise AIMS scores for each visit. The occurrence of neurological side effects will be assessed by looking at the changes in scores from baseline to post-baseline visits.

For each item on the AIMS scale, the number (and percentage) of subjects with a worse score at any post-baseline visit, compared to baseline, will be presented in Table 6.7.3.1.

7. DATA SAFETY MONITORING BOARD (DSMB)

A Data Safety Monitoring Board (DSMB) will monitor the conduct and safety of the study on a quarterly basis. Appendix 13.2 and 13.3 respectively contain the DSMB reports for the two meetings.

8. CHANGES IN CONDUCT OR PLANNED ANALYSES FROM THE PROTOCOL

Describe any changes to statistical methods section in the protocol before database lock. Provide the reasons for the changes. Some changes may require an amendment to the protocol.

Any changes to the statistical analysis plan after database lock should be addressed in a separate document. That document will be approved separately and included as an addendum to the final SAP.

8. PROGRAMMING SPECIFICATIONS

All summary tables, data listings, figures and other statistical output will be produced with the SAS system (version 9.2) and will be incorporated into a MS Word document for easy integration into the CSR production process. Summary tables, data listings, and figures will be produced in the order that they appear in the textual sections of the plan.

The SAS generated output will adhere to the following specifications.

8.1 FORMAT OF TABLES AND LISTINGS

Tables and listings will be produced in landscape orientation. To ensure the print window is usable for both A4 paper size (21 x 29.7 cm; 8.27 x 11.69 inches) and US letter paper size (21.59 x 27.94 cm; 8.5 x 11 inches), the following page size and margins will be used:

- Print window: 15.88 x 22.61 cm (6.25 x 8.9 inches)
- Top and bottom margins approximately:
 - A4: 2.54 cm (1 inch);
 - US: 2.85 cm (1.12 inches).
- Left and right margins approximately:
 - A4: 3.56 cm (1.4 inches);
 - US: 2.54 cm (1 inch).

A fixed space font (Courier New or SAS Monospace) with point size 9 will be used for all tables and listings. Under very limited circumstances, reducing the point size to 8 or 7.5 for a listing may be considered if the reduction is absolutely necessary to fit all columns on one page, and splitting the listing into two or more pages is not a viable option.

8.1.1 Title of a Table/Listing

The first line of the title will immediately follow the header line (i.e., no blank line in between). The title of a table/listing will be centered. The first letter of each imperative word will be capitalized. Up to 6 lines of the page are available to enter the title. (Note: There will be no blank title lines.)

The title will state the table/listing number, describe the table/listing briefly, and describe the population that is included in the table/listing, i.e.:

- Line 1 of title: Table xx.x.
- Line 2 of title: *Main title*
- Line 3 of title (optional): *Subtitle*
- Line 4 of title: XXX Population

If Line 3 is not utilized, then Line 4 will be moved up.

The table/listing numbering will be consecutive, with no skipping of numbers. Up to 5 levels of numbering (i.e., xx.x.x.x.x or xx.x.x.x.x) are allowed. If the same table/listing is produced for multiple analysis populations (e.g., ITT Population and restricted ITT Population) or data imputations (e.g., Observed Data and LOCF Data), the resulting multiple tables/listings should share the same table/listing number, except for the last level, which will be consecutively numbered 1, 2, 3, ..., t where t is the total number of tables/listings generated (e.g., 4.2.1 for ITT Population and 4.2.2 for restricted ITT Population).

For numeric variables, the appropriate unit will be added to the column heading. For

frequency tables, only those categories for which there is at least one subject represented in one or more groups should be included. Within data listings, subjects will be ordered by treatment, weight category at baseline, center number, subject number, visit, and time of collection (if available).

Verbose titles should be avoided. In the case where a title line is too wide for the page, then the title line will wrap on to the next line, and all subsequent lines will increment by one.

If there is stratification or subgrouping of the population (e.g., Sex) with summaries to be presented for each subgroup on a separate page, the subgrouping label on a page (e.g., Males) will appear, left-aligned with the body of the table/listing, on the line immediately below the last title line.

There will be a solid horizontal line across the page immediately below the last title line (or the subgroup label, if present), as wide as the body of the table/listing.

8.1.2 Footnotes to a Table/Listing

There will be a solid horizontal line across the page, as wide as the upper horizontal line, signifying the end of the body of the table/listing for that page. Footnotes are immediately below this horizontal line, with the exception of the documentation line, which appears on the bottom line of the page. Footnotes will be left-aligned with the body of the table/listing. If the footnote is a complete sentence, then the usual sentence construction will be followed. If the footnote is a single word or a phrase, then the first letter of the first word will be capitalized. Up to 9 lines of the page are available to enter footnotes.

For a table, the first footnote will name the listing(s) where the data used in the table came from, in the following format:

Source: Listing xx.x

Footnotes that apply to the table/listing in general will precede footnotes that apply to a specific item (e.g., title line, row label, column header, specific count, descriptive statistic, p-value, or data) on the table/listing. An example of a general footnote is as follows: "A subject who has the same TESS more than once during the study was counted once in the total number of subjects per system organ class calculation." An example of an item-specific footnote is as follows: "Significant at the 0.050 level".

The use of superscripting in footnotes is not recommended. If there is only one item-specific footnote on a table/listing, one of the symbols #, *, and @ will be used to tag the item, with a single blank space between the item and the symbol. In general, the asterisk will be reserved for tagging items related to the presentation of p-values. The footnote will begin with the symbol, followed by a single blank space, and then the footnote text, e.g.:

footnote text here

If there are multiple item-specific footnotes on a table/listing, "(x)" will be used to tag each item, with the x's being either all numbers (1, 2, 3, etc.) or all letters (a, b, c, etc.), and with a single blank space between the item and the corresponding "(x)". The footnote will begin with the "(x)", followed by a single blank space, and then the footnote text, e.g.:

(x) *footnote text here*

The use of self-explanatory or commonly used abbreviations to tag an item for footnoting may supersede the conventions described in the two preceding paragraphs. Examples of commonly used abbreviations include the following: H=Above upper normal limit, W=Within normal limits, and L=Below lower normal limit; ND=Not done; N/A=Not applicable; and NAV=Not available. Note that in these examples, the letters are not in parentheses and have the equal sign connecting the letters with the footnote text.

When a general footnote exceeds one line in length, the text will wrap on to the next line, with no indentation if there is only one general footnote (excluding the source footnote) and with two-space indentation if there are more than one general footnote. When an item-specific footnote exceeds one line in length, the lines after the first one will be left-aligned with the first line, minus the "(x)", e.g.:

(x) *first line of footnote text here*
second line of footnote text here

8.1.3 Header and Footer

Although not depicted on the shell outputs, every output will have the following Header:

Supernus Pharmaceuticals, Inc.
Protocol No.: 810P201

Page x of xx

and the following Footer:

Program: Programname.sas DDMMYYYY HH:MM

Produced: DDMMYYYY HH:MM

8.2 DATA FORMAT

Unless otherwise specified, the estimated mean and median for a set of values will be printed out to one more decimal place than the individual units of measurement, and the standard deviation and coefficient of variation will be printed out to one additional place further. P-values will be given with 3 decimals. P-values < .001 will be shown as "<0.001". All fractional numeric values will be printed with a zero to the left of the decimal point (e.g., 0.12, 0.3 etc.). Unless otherwise specified, percentage values will be printed with one digit to the right of the decimal point (e.g., 52.3%, 8.9% etc.). Dates will be displayed using the ISO 8601 format as required for Clinical Data Interchange Standards Consortium (CDISC) standards. Dates will be presented as DDMMYYYY and time values will be presented as HH:MM:SS or HH:MM.

8.3 CODING LISTS

The coding of the data is performed with the following coding lists:

Data	Coding list / Version
Adverse events	MedDRA / Version 11.1
Medication names	WHO Drug Dictionary/ December 2008

9. SUMMARY TABLES, DATA LISTINGS AND FIGURES (TLFS)

Shells of summary tables and data listings are presented as separate documents in order to provide a framework for the display of data and results of statistical analyses for this study. These shells may change due to unforeseen circumstances. There are no shells for figures.

11. FINAL VERSION REVISION HISTORY

Date of Revision	Author	Summary of Change(s) From Final Version 1.0

12. APPENDICES

12.1 APPENDIX I: DATA REVIEW MEETING MINUTES

12.2 APPENDIX II: REPORT TO THE FIRST MEETING OF THE DSMB

12.3 APPENDIX III: REPORT TO THE SECOND MEETING OF THE DSMB
